The number and percentage of subjects that met the iron management criteria during the study while on treatment will be summarized by treatment group for each 3-month period of the study, the first year and across the entire study. There are two types of iron management thresholds: the first type requires that iron therapy be administered if subjects have ferritin and/or TSAT values that are too low; the second type requires that all iron (excluding multivitamins) must be stopped if ferritin and/or TSAT values are too high. It is also possible for a subject to meet starting and stopping criteria on the same

200807

day with a low ferritin and a high TSAT. These subjects will also be summarized (see Section 10.6.3). Assessment of meeting iron management thresholds will be made based on central laboratory data values at the scheduled visits for ferritin and TSAT assessments, according to the schedule outlined in the Time and Events table (see Section 10.2.1). Further, the subjects who met the threshold requiring iron administration to start or stop while on IV iron will be grouped by the action taken with IV iron therapy in the 8 weeks following the date the threshold was met (i.e., starting or increasing iron therapy, maintaining existing iron therapy, receiving no iron therapy, stopping or decreasing iron therapy with no increase, Section 10.6.3) according to concomitant medication records for IV iron.

The number and percentage of subjects that reduced IV iron supplementation relative to baseline during the EP while on treatment will be summarized by treatment group (see Section 10.6.3).

RBC and Whole Blood Transfusions

Summary and analysis tables will use the ITT population.

The total number of on-treatment RBC and whole blood transfusion events, transfusions and units for each subject will be derived as described in Section 10.6.3.

The number of on-treatment RBC and whole blood transfusion events per subject, the number of subjects with at least one RBC and whole blood transfusion event, and total number of RBC and whole blood transfusion events will be summarized.

The number of on-treatment RBC and whole blood transfusions events per 100 patient years will be summarized by treatment group.

The number of on-treatment RBC and whole blood transfusions per 100 patient years will be summarized by treatment group.

The number of on-treatment RBC and whole blood units per 100 patient years will be summarized by treatment group.

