10.6.3.2. Iron Endpoints

Iro	n Endpoints				
Iro	Iron Medications				
•	 During the study, subjects may be receiving iron in multiple routes, including: IV iron Oral iron Other iron (including intramuscular, subcutaneous, and hemodialysis/dialysate) Note: The iron route categories above will be determined using the route on the 				
•	Prior/Concomitant Medication – Iron Therapy record. In addition, ferric citrate records recorded on the Prior/Concomitant Medication – Metabolic Bone Disease Therapy eCRF form will also be summarized as oral iron use.				
Ba	seline Iron Use				
•	The number and percentage of subjects in the following iron use categories at baseline will be summarized: IV iron use only Oral iron use only Other iron use only IV and oral iron use only IV and other iron use only IV and other iron use only Oral and other iron use only Oral and other iron use only IV, oral, and other iron use No iron use When determining baseline iron use, the gap factors mentioned below in the IV iron standardization algorithm will be applied to the end date for each iron record, and the baseline period of 16 weeks before the Randomization date until the day before the Randomization date will also be used.				
Sta	andardized IV Iron Dose (mg/week) to Determine Iron Management Action				
•	In order to compare between IV iron records, to determine the action taken with IV iron therapy in the 8 weeks following the date the IV management threshold was met, the dose of IV iron in each associated record will be standardized in terms of mg/month.				
•	 IV iron therapy concomitant medication records that occur or are ongoing during the 8 weeks following the date the IV management threshold was met (inclusive), will be selected and ordered by start and end date. If there is a record has a start date on the date the IV management threshold was met, and a prior record has an end date on the day before the IV management threshold was met, this prior record will be selected and considered as well. 				

200807

Iron En	dpoints
---------	---------

• The standardization will be carried out with the following formula:

• Standardized IV iron dose (mg/week) = IV iron drug dose (mg) * frequency

Note: Frequency defined as follows:

Frequency (from eCRF)	Frequency (for standardization formula)
2 times per week	2
3 times per week	3
4 times per week	4
5 times per week	5
BID	14
Once daily	7
One time dose	1
Every 12 Hours	14
Every 2 weeks	0.5
Every 4 weeks	0.25
Once a month	0.23

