		lized to obtain a continuous single	
-	•	he Randomization date to the Wee	
ubjec		fore their first RBC or whole blood t	
		o are randomized but never treated	
.	• ·	V iron from Randomization to Weel	
		edication records that occur or are ion date – 16 weeks to the Week 5	
	rdered by start date and		
	•	ried out with the following formula:	
0		ose (mg/week) = IV iron drug dose	(ma) * frequency
0			(mg) nequency
Fred	uency and Gap Factors	defined as follows:	
	equency (from eCRF)	Frequency	Gap Factor
		(for standardization formula)	-
2	times per week	0	0 E dava

2

2.5 days

2 times per week

200807

Iron E	ndpoints		
	3 times per week	3	1.33 days
	4 times per week	4	0.75 day
	5 times per week	5	0.4 day
	BID	14	0 days
	Once daily	7	0 days
	One time dose	1	n/a
	Every 12 Hours	14	0 days
	Every 2 weeks	0.5	13 days
	Every 4 weeks	0.25	27 days
	Once a month	0.23	29 days
	Once a week	1	6 days
	TID	21	0 days

• If the frequency of the record is not 'one time dose', then duration is calculated as follows:

 If the concomitant medication record start date > earliest of (treatment stop date + 1 and Week 52 visit date), the duration of the record is 0.

• If the concomitant medication record end date + gap factor < Randomization date, the duration of the record is 0.

 o If the concomitant medication record end date + gap factor ≥ Randomization date or the record is ongoing, the duration of the record will be calculated as Stop Date – Start Date +1 day where:

- Start date will be the latest of (concomitant medication record start date, randomization date, treatment start date).
- Stop date will be the earliest of (concomitant medication record stop date + gap factor, first transfusion date (RBC or whole blood), treatment stop date + 1, and the Week 52 visit date).
- If the frequency of the record is 'one time dose', then:
 - If concomitant medication record start date < treatment start date, or if earliest of (first transfusion date (RBC or whole blood), treatment stop date +1 and Week 52 visit date)
 < concomitant medication record start date, then duration of the record is 0.
 - o If latest of (Randomization date, treatment start date) ≤ concomitant medication record start date ≤ earliest of (first transfusion date (RBC or whole blood), treatment stop date + 1 and Week 52 visit date), then:
 - Frequency (for standardization formula) = 1
 - Duration = 7 days
- The total dose for each IV iron record will be: Standardized dose*duration/7 days

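### The score that classifies iron-management action counts a one-time IV iron dose as a weekly order, so a cut in IV iron can be shown as increasing or maintaining in an exploratory table

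*SAP*

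**What the plan says.** Section 8.1.3.2 (Iron Parameters) groups subjects who met a start or stop threshold while on IV iron by what happened to IV iron over the next 8 weeks. The groups are "starting or increasing iron therapy, maintaining existing iron therapy, receiving no iron therapy, stopping or decreasing iron therapy with no increase". It refers to section 10.6.3 for details.

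Section 10.6.3.2 supplies the score for that comparison, introduced with "In order to compare between IV iron records, to determine the action taken with IV iron therapy". The formula is "Standardized IV iron dose (mg/week) = IV iron drug dose (mg) * frequency". The frequency table contains "One time dose 1" and gives once a week the same factor, 1. The records selected are "IV iron therapy concomitant medication records that occur or are ongoing during the 8 weeks following the date the IV management threshold was met". One earlier record is added only if it ends the day before the threshold date and another starts on that date. This block has no duration, no gap factor and no count of records. Its heading and formula are in mg/week, but its introductory text says mg/month.

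The other three dose algorithms in 10.6.3.2 (baseline, randomization to Week 52, and Weeks 28 to 52) use the same factor for a one-time record but add "Duration = 7 days". They take each record's total as "Standardized dose*duration/7 days".

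**The concern.** Factor 1 is harmless in the averaging algorithms because the 7-day duration turns it back into the dose given. In the action score that step is missing, so one administration carries the same weight as an order repeated every week of the window.

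The table is meant to show what was done with IV iron after a threshold was met. Its stop/decrease group excludes anyone with an increase, so one spurious increase moves a subject out of that group and into the opposite one. The same happens after a start threshold, where a fall in iron would be displayed as an increase.

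**Working it through.** **Inputs.** From section 10.6.3.2: score = dose × frequency, with factors once a week 1, one-time dose 1, every 2 weeks 0.5, once a month 0.23, three times a week 3. The SAP gives no dose sizes, so the 100 and 200 mg doses below are assumptions. The SAP also does not say how scores map to categories; I take higher = increasing, equal = maintaining, lower = decreasing. There is no figure in the plan to reproduce.

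**One-time dose in the two kinds of algorithm.**
- Averaging algorithms: 100 mg × 1 × 7/7 = 100 mg, the dose given.
- Action score: 100 mg × 1 = 100 mg/week, the same as a standing 100 mg weekly order, which delivers 100 × 8 = 800 mg over 8 weeks.

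**General condition.** Let an order score S mg/week, so that 8 weeks of it deliver 8S. Let it end and be followed by one dose D, the only later IV iron in the window. The score reads increasing when D > S and maintaining when D = S. The iron received falls whenever D < 8S. So every D from S up to, but not including, 8S is given a label that does not match the fall.

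**Examples (assumed doses).**

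| Order, then one single dose | Scores | Label | 8-week iron | Change |
|---|---|---|---|---|
| 100 mg weekly, then 200 mg | 100 → 200 | increasing | 800 → 200 mg | −75% |
| 100 mg every 2 weeks, then 100 mg | 50 → 100 | increasing | 400 → 100 mg | −75% |
| 200 mg once a month, then 100 mg | 46 → 100 | increasing | 368 → 100 mg | −72.8% |
| 100 mg weekly, then 100 mg | 100 → 100 | maintaining | 800 → 100 mg | −87.5% |
| 100 mg three times a week, then 100 mg | 300 → 100 | decreasing | 2,400 → 100 mg | −95.8% |

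The last row is labelled correctly, because D < S.

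**Several one-time records.** Each 100 mg one-time record in the window scores 100 whether there are two or eight of them, so the comparison cannot tell 200 mg from 800 mg.

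**With the dose counted as given.** A single 200 mg dose over 8 weeks is 200/8 = 25 mg/week, and a single 100 mg dose is 12.5 mg/week. The first two rows become 100 → 25 and 50 → 12.5, both decreases.

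**The case against.** Four points can be made for the plan as it stands.

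- *A new dose after a stop threshold may rightly count as an action.* The first category pools starting with increasing, and a fresh administration after the stop criteria are met is arguably not a clean stop. This has force for the stop threshold. It does not cover the start threshold, where the same history would appear as increasing after a 75% cut.
- *The category rule is not written down.* This is true, and the labels above rest on the natural reading. The silence is itself something to repair.
- *A before-and-after total could hide a restart.* This is also true. An order of 100 mg/week stopped for six weeks and then restarted at 200 mg/week for two weeks totals 400 mg against 800 mg, and the restart disappears. A total therefore needs a separate flag beside it.
- *The mg/week versus mg/month slip changes no result*, since every record goes through the same formula. Agreed; it is only a label.

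Two stronger readings are tempting, and the document does not support them. A reader might infer that stopping a standing order is in itself reported as an increase. It is not: a later single dose larger than S must be recorded in the window. A reader might also infer that a drop from many single doses before the threshold to one afterwards is reported as maintaining. The selection rule leaves out most earlier one-time records, so a lone later record normally has no comparator. Equal scores need at least two equal one-time records among those selected.

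**Conclusion.** The concern holds in a limited form. The action score treats a single administration as a weekly order, and for any single dose D with S ≤ D < 8S the label does not match the fall in iron received. In the assumed examples, totals that fall by about 73% to 87.5% are shown as increasing or maintaining. This rests on the assumed mapping from scores to categories, on the order being among the selected records, and on the single dose being the only later IV iron in the window. The SAP does not say how common one-time records are, so the number of subjects affected cannot be estimated.

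The reach is small. Only the descriptive breakdown by action taken is affected, and it belongs to an exploratory endpoint with no planned testing (section 2.2). A reader might infer that the IV iron treatment comparison is contaminated. It is not: the principal secondary endpoint uses the randomization-to-Week 52 algorithm, which gives a one-time dose its 7-day duration. Counts of subjects meeting the iron criteria do not use the score either. This is a worthwhile correction, not a serious defect.

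**What to change.** In the action block of section 10.6.3.2:

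1. Count each one-time record by the dose actually given, using the 7-day duration as in the other three algorithms.
2. Sum IV iron over the 8 weeks after the threshold date, express it as mg/week, and compare it with the weekly rate before that date. State how the earlier rate is obtained, since the present selection leaves out most earlier records.
3. Write out the rule that maps the comparison to the four categories, including the tolerance for maintaining.
4. Keep a separate flag for any new start or restart in the window, so that a total does not hide it.
5. Change mg/month to mg/week in the introductory text.

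The cost is a short wording change and a little programming. The existing duration and gap-factor logic is a starting point, but it was written for fixed periods and the post-randomization versions cut off at transfusion and treatment stop, so it needs some adaptation. The tolerance is a choice with no source in the document and should be fixed before unblinding. The change concerns only how recorded iron data are classified.

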10.6.3.3. Time to Rescue

Time	to Stopping Randomized Treatment Due to Meeting Rescue Criteria
	ng Rescue Evaluation Criteria and Rescue Criteria
Si is su su Si di ou su su • S	ubjects meeting evaluation criteria for rescue are identified from the Rescue Treatment eCRF. ubjects with a record on this form are considered to have met evaluation criteria for rescue. It possible that a subject could be evaluated for rescue more than once, and in that case a ubject would have multiple records on this form. ubjects unable to be evaluated for rescue are subjects who met evaluation criteria for rescue, ut were unable to be assessed at the 4 week check (e.g., subjects who died, permanently scontinued randomized treatment or withdrew from the study before the 4 week check). The utcome of initial intervention eCRF field on the Rescue Treatment eCRF will be blank for these ubjects. ubjects meeting rescue are identified by the response 'Met rescue criteria' to the outcome of itial intervention question on the Rescue Treatment eCRF.
Event	
	reatment stop date when the primary reason and subreason for randomized treatment stop re: • Primary reason: Subject reached protocol-defined stopping criteria • Subreason: Rescue
Gene	ral Definitions
• C • R w ce	ime to event (days) = date of event – randomization date +1 ensored time (days) = censoring date – randomization date + 1 escue person years = (cumulative total time to stopping randomized treatment for subjects ho stopped randomized treatment due to meeting rescue criteria + cumulative total of ensoring time for subjects who did not stop randomized treatment due to meeting rescue riteria) / 365.25
 R ra R (p 	escue incidence rate (per 100 person years) = (100 * number of subjects who stopped andomized treatment due to meeting rescue criteria) / rescue person years escue absolute rate difference (per 100 person years) = daprodustat rescue incidence rate per 100 person years) – rhEPO rescue incidence rate (per 100 person years)
	Period for Treatment Discontinuation
 define For standard For standard 	eriod for treatment discontinuation begins at randomization. The end of this time period is ed as follows: or subjects who did not take randomized treatment, use the date of randomization or subjects whose treatment stop date is missing and who took randomized treatment, use cudy conclusion date or subjects either continuing on study past treatment stop date or completing/withdrawing on the same day as treatment stop date, use treatment stop date
Any e perioc	vents that occurred before the start of this time period are considered to be prior to the time d for treatment discontinuation, and any endpoints that occurred after the end of this time d are considered to be post the time period for treatment discontinuation.

200807

10.6.3.4. RBC and Whole Blood Transfusion Endpoints

Number of RBC and Whole Blood Transfusions The number of transfusions associated with each RBC and Whole Blood Transfusion record is determined by the frequency, start date, end date and number of units, as described below. Only on-treatment transfusions are included. "End date" below refers to the end date defined

- for the transfusion, or the end of the on-treatment period, if sooner (see Section 10.6.3).
 For records with a frequency of "Once only" or "Continuous infusion", each record is
- For records with a frequency of "Once only" or "Continuous infusion", each record is considered to be a single transfusion (regardless of start and end dates or number of units).
- For records with a frequency of "Once daily", the number of transfusions will equal the duration (end date – start date +1).
- For records with a frequency of "PRN", or where the frequency is unknown, the number of transfusions for each record will be equal to the number of units recorded.
- For other transfusion records, the number of transfusions will equal the duration (end date start date +1) times a multiplier, as defined below: The number of transfusions should be rounded up to the nearest integer.

Frequency	Multiplier	
QM	0.033	
Every 2 weeks	0.071	
Once a week	0.14	
Q4D	0.25	
2 times per week	0.29	
Q3D	0.33	
3 times per week	0.43	
Every other day	0.5	
4 times per week	0.57	
5 times per week	0.71	
BID	2	
Q12H	2	
TID	3	
Q8H	3	
QID	4	
Q6H	4	
5 times per day	5	
Q4H	6	
Number of RBC and Whole Blood Transfusion Events		

Number of RBC and Whole Blood Transfusion Events

- RBC and Whole Blood Transfusion Events are defined by grouping together on-treatment transfusion records.
- Transfusion records are grouped into the same Transfusion Event if the transfusion start/end dates match with or are contained within an Admission/Discharge period, (based on the Hospitalization page in the eCRF)
- For example, the following transfusion records would be grouped into a single Transfusion

200807

Event, because each transfusion is contained within the same hospital admission/discharge period:

Dose	Frequency	Transfusion Dates		Hospitalisation		Comment
		Start Date	End Date	Admission	Discharge	
1 unit	Once only	16FEB2019	16FEB2019	15FEB2019	26FEB2019	1 Transufsion
1 unit	Once only	19FEB2019	19FEB2019	15FEB2019	26FEB2019	Event

- Transfusion records not matching with an Admission/Discharge period are considered to be the same Transfusion Event if the gap between transfusions is 5 days or less, with further details provided below. For any subject where the frequency is PRN and the transfusion start date ≠ end date, the dates of individual transfusions are unknown and the number of transfusion events will be counted as one.
- In the case of a sequence of more than two transfusions, transfusions are considered to be the same Transfusion Event if the gap between each transfusion and the start date of the first transfusion in the sequence (the "anchor" transfusion) is 5 days or less. The first transfusion that is greater than 5 days after the "anchor" transfusion is not included in the Transfusion Event, and it becomes the new "anchor" transfusion for a new Transfusion Event.
- In the example below, transfusion records 1 and 2 would be grouped into a single Transfusion Event, because the gap between the transfusions (17JAN2019 to 18JAN2019) was 5 days or less. Record 3 falls outside this Transfusion Event because the gap between the start date (22JAN2019) and the previous anchor date (16JAN2019) is more than 5 days. Therefore 22JAN2019 becomes the new "anchor" transfusion used to define the next Transfusion Event. This pattern is repeated, if necessary. N.B. "anchor" transfusions are shown in bold.

#	Dose	Frequency	Transfusion Dates		Comment
			Start Date	End Date	
1	1 unit	Once only	16JAN2019	16JAN2019	1 Transfusion Event
2	1 unit	Once only	19JAN2019	19JAN2019	
3	1 unit	Once only	22JAN2019	22JAN2019	1 Transfusion Event
4	1 unit	Once only	25JAN2019	25JAN2019	
5	1 unit	Once only	28JAN2019	28JAN2019	1 Transfusion Event

Number of Units

- The number of RBC and whole blood units are derived from blood transfusion records. The number of units associated with each record is determined by the frequency, start date, end date and dose (i.e. number of units recorded), as described below:
- Only units associated with on-treatment transfusions are included. "End date" below refers to the end date defined for the transfusion, or the end of the on-treatment period, if sooner (see Section 10.4.1).
- For records with the frequency recorded as "Once only" or "Continuous infusion", the total number of units associated with each record is the number of units recorded (regardless of start and end dates)
- For records with the frequency recorded as "Once daily", the total number of units associated with each record will equal the number of units recorded multiplied by the duration (end date –

200807

start date +1)

- For records with the frequency recorded as "PRN", the total number of units will be equal to the number of units recorded (regardless of start and end dates)
- For other records, the number of units will be equal to the number of units recorded multiplied by the duration (end date start date +1) times a multiplier, as defined for Number of RBC and Whole Blood Transfusions above
- The table below provides multipliers for converting various reported units to Units (which should be rounded up to the nearest integer). For example, a transfusion of 450ml represents a single unit:

(450 x 0.0025) = 1.125 (rounded up to 2 Units)

Reported Units	Multiplier
Units	1
Milliliters (ml or CC)	0.0025
Milligram (mg)	0.0025
Milligrams/milliliters (mg/ml)	0.0025

- Where a non-integer number of units has been entered on the eCRF, this will be rounded up to the nearest integer prior to any subsequent derivation (if necessary).
- Where a transfusion record has been entered with a missing number of units, the number of units associated with the record will be assumed to be 1 unit.

Evaluation Period (Weeks 28 to 52)

- Only transfusion events with a start date from date of week 28 visit to the date of the week 52 visit will be included
- Patient Years (PY) = (cumulative total time from date of week 28 visit to the date of the week 52 visit, for subjects who did not withdraw from randomized treatment during the evaluation period + cumulative time from date of week 28 visit to the date of withdrawal from randomized treatment, for subjects who withdrew from randomized treatment during the evaluation period) / 365.25
- Transfusion Events per 100 PY = (100 * number of on-treatment RBC or whole blood transfusion events during the evaluation period) / Patient Years (PY)
- Transfusions per 100 PY = (100 * number of on-treatment RBC or whole blood transfusions during the evaluation period) / Patient Years (PY)
- Units per 100 PY = (100 * number of on-treatment RBC or whole blood transfusion units during the evaluation period) / Patient Years (PY)

Randomization to Week 52

- Only transfusion events with a start date from the date of randomization to the date of the week 52 visit will be included
- Patient Years (PY) = (cumulative total time from date of randomization to the date of the week 52 visit, for subjects who did not withdraw from randomized treatment prior to week 52 + cumulative time from date of randomization to the date of withdrawal from randomized treatment, for subjects who withdrew from randomized treatment prior to week 52) / 365.25
- Transfusion Events per 100 PY = (100 * number of on-treatment RBC or whole blood transfusion events from the date of randomization to the date of the week 52 visit) / Patient Years (PY)

 Transfusions per 100 PY = (100 * number of on-treatment RBC or whole blood transfusions from the date of randomization to the date of the week 52 visit) / Patient Years (PY) Units per 100 PY = (100 * number of on-treatment RBC or whole blood transfusion units from the date of randomization to the date of the week 52 visit) / Patient Years (PY)
Randomization to End of Treatment
• Person Years (PY) = (cumulative total time from date of randomization to the study conclusion date, for subjects who did not withdraw from randomized treatment + cumulative time from date of randomization to the date of withdrawal from randomized treatment, for subjects who withdrew from randomized treatment) / 365.25
 Transfusion Events per 100 PY = (100 * number of on-treatment RBC or whole blood transfusion events from the date of randomization to the date of study conclusion or withdrawal from treatment) / Person Years (PY)
 Transfusions per 100 PY = (100 * number of on-treatment RBC or whole blood transfusions from the date of randomization to the date of study conclusion or withdrawal from treatment) / Person Years (PY)
 Units per 100 PY = (100 * number of on-treatment RBC or whole blood transfusion units from the date of randomization to the date of study conclusion or withdrawal from treatment) / Person Years (PY)
Time to First On-Treatment RBC or Whole Blood Transfusion
• Event Date = Start date for the first on-treatment RBC or whole blood transfusion received after treatment start date
• Censoring Date = date of stopping randomized treatment for subjects who stopped randomized treatment, or date of study completion for subjects who did not stop randomized treatment
• Time to event (days) = date of event – treatment start date +1
Censored time (days) = censoring date – treatment start date + 1
 Person years (PY) = (cumulative total time to event date, for subjects who received at least one on-treatment RBC or whole blood transfusion + cumulative total of censoring time for subjects who did not receive at least one on-treatment RBC or whole blood transfusion) / 365.25
 Incidence rate per 100 PY = (100 * number of subjects who received at least one on-treatment RBC or whole blood transfusion) / person years
Absolute rate difference (per 100 person years) = daprodustat incidence rate (per 100 person years) – rhEPO incidence rate (per 100 person years)
Time Period for On-Treatment Transfusions
• The period for capturing on-treatment transfusions begins on the treatment start date +1day. The end of this time period is defined as follows:
 For subjects continuing on study past the (treatment stop date + 1day), use (treatment stop date + 1day)
 For subjects whose study withdrawal/completion date is on or before (treatment stop date + 1day), use date of study withdrawal/completion
Model Specification
 Analysis of time to first RBC or whole blood transfusion will be performed using an analysis model identical to that described for the co-primary MACE analysis (Section 7.2.2) for the evaluation of superiority.
Analysis will include only transfusion occurring during the on-treatment period

200807

Model Results Presentation

- The model results presentation will be identical to the co-primary MACE model results, with the following exception:
- A single one-sided p-value for the test of superiority of daprodustat vs. rhEPO will be presented (i.e. there will be no test for non-inferiority).
- A Kaplan-Meier plot will be produced showing the survival function for time to first RBC or whole blood transfusion.

